1. INTRODUCTION

The purpose of this reporting and analysis plan (RAP) is to describe the analyses to be included in the Clinical Study Report for study BTZ116577.

Revision Chronology:	
Version	Date
Original	05 Oct 2022
Amendment No. 1	16 Mar 2023

Updates include:
 
 • Minor formatting and typographical updates. • Alignment with changes in Protocol Amendment 2: 
 ○ Increased the total number of enrolled participants from approximately 600 to approximately 620 (Section 2.3). ○ Primary analysis population (Micro ITT) updated with ceftriaxone susceptibility evaluated using EUCAST breakpoints (Section 4). • Clarified primary and secondary efficacy estimands variable/endpoint attribute to state that for microbiological success participant must not receive other systemic antimicrobials prior to the TOC assessment (Section 2.2.1). • Clarified text on declaration of superiority (Section 2.4). • Clarified that all Microbiologically Evaluable analysis populations include the condition that actual treatment is the same as randomized (Section 4). • Added Micro-ITT CLSI Analysis Population (Section 4) for the sensitivity analysis for the primary analysis including isolates identified as resistant by EUCAST but susceptible by CLSI (Section 7.1.6.2). • Removed references to Lu K., Guo H. Multiple imputation analysis of Miettinen-Nurminen interval for difference in proportions, Pharmaceutical Statistics. 2021;1–13 as this method will not be used (Section 7.1.6.1, Section 7.1.6.2 and Section 11). • Updated confidence interval methods for pooled estimates (after using Rubin’s rules) to Wald-type confidence intervals for both the multiple-imputation and tipping point sensitivity analyses (Section 7.1.6.2). • Clarified that there will be no multiplicity adjustment or formal hypothesis testing of secondary or exploratory endpoints, but that confidence intervals may be included for descriptive purposes (Section 7.2.6 and Section 7.3.3). • Added Adverse Reactions analyses (Section 8.5). • Clarified efficacy analyses for Benefit/Risk (Section 10). • Clarification on “Out of stability” isolates for the Keepers file (Section 12.4.2). • Clarification on the calculation of MIC₅₀ and MIC₉₀ (Section 12.4.2). • Removed imputation rules for laboratory parameter character values (Section 12.4.3). • Removal of laboratory values not relevant to this study (Section 12.7). • Added note regarding All Analyses Complete (AAC) (Section 12.9.3). 	

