Amendment No. 2	13 Oct 2023

Updates Include:
 
 • Minor formatting and typographical updates throughout. • Added a note for clarification that “systemic antimicrobials before the TOC Visit” in the intercurrent event strategy for the efficacy estimands in Table refers to “other systemic antimicrobials” i.e., excluding the investigational product (Section 2.2.1). • For the Micro-ITT population, ceftriaxone susceptibility determination has been changed to CLSI from EUCAST guidelines in order to meet regulatory submission requirements (Section 4). 
Additionally:
	

- Micro-ITT CLSI population amended to Micro-ITT EU population (Section 4).
 - References to EUCAST in primary analysis updated to CLSI (Section 7.1).
 - Sensitivity analysis for the primary analysis changed from being based on Micro-ITT CLSI to Micro-ITT EU population (Section 7.1.6.2) and corresponding text relating to determination of ceftriaxone susceptibility by disk diffusion (CLSI guidelines) added.
 - Provision added for the reproduction of any summaries or listings using populations based on CLSI guidelines to be repeated on the equivalent population but using EUCAST guidelines for the determination of ceftriaxone susceptibility (Section 4 and Section 7).
- Added clarification that the Micro-ITT population will be used for Study Population summaries as well as Efficacy summaries (Section 4).
 - Added clarification that for participants with more than 1 NG isolate recovered at baseline from the same body site, all of the isolates must be susceptible to ceftriaxone for that participant to be included in the Micro-ITT populations (Section 4).
 - Added clarification on the handling of out of stability NG negative samples at the TOC visit for the purposes of Microbiologically Evaluable populations (Section 4).
 - Added clarification that final determination of population inclusion will be performed after final data extraction and that two pre-specified criteria for ME populations will be applied on unblinded data (Section 4).
 - Added clarification that the Micro-ITT CAPA population may be defined, and corresponding supplementary analysis be conducted, if one or more sites/investigators had a CAPA that stipulates that a supplementary analysis should be conducted, as agreed by a GSK multidisciplinary team (Section 4 and Section 7.1.6.3).
 - Summary of randomized versus actual pooled strata added (Section 5.4.1).

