4. ANALYSIS POPULATIONS

Population	Definition / Criteria	Analyses Evaluated
Screened Population	
 • All participants who were screened for eligibility. 	
 • Study Population
Intent-to-Treat (ITT) Population	
 • All participants randomly assigned to study treatment. • Participants will be analyzed according to their randomized treatment arm 	
 • Study Population • Efficacy
Microbiological ITT (Micro-ITT) Population	
 • All participants randomly assigned to study treatment who receive at least 1 dose of study treatment and have confirmed NG isolated that is ceftriaxone-susceptible (based on CLSI breakpoints) from baseline culture of their urogenital specimen. • Participants will be analyzed according to their randomized study treatment arm. • This is the primary analysis population. 	
 • Study Population • Efficacy
Microbiological ITT FDA (Micro-ITT FDA) Population	
 • All participants randomly assigned to study treatment who receive at least 1 dose of study treatment and have confirmed NG isolated that is ceftriaxone-susceptible (based on CLSI breakpoints) from baseline culture of their urogenital specimen plus participants who have missing susceptibility and NG isolated at the local laboratory, identified using a recognized method. • Participants will be analyzed according to their randomized study treatment arm. 	
 • Study Population

Population	Definition / Criteria	Analyses Evaluated
Microbiological ITT EU (Micro-ITT EU) Population	
 • All participants who meet the definition of the Micro-ITT population and any participants randomly assigned to study treatment who receive at least 1 dose of study treatment and have confirmed NG isolated that is ceftriaxone-susceptible (based on EUCAST breakpoints) from baseline culture of their urogenital specimen. • Participants will be analyzed according to their randomized study treatment arm. 	
 • Efficacy

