If for a pair of assumed response rates there is zero between imputation variance, e.g., if there are no missing data to impute, then the methods described above for calculating the proportion of successes, risk difference and associated standard errors, will be applied to a single instance of the complete data set and it will not be necessary to combine estimated quantities across imputations. Note also that tipping point analysis may be repeated with a greater number of imputations (if necessary over a smaller, refined grid range), if tipping points are considered to be sensitive to the random number seed and/or number of imputations. Furthermore, if the extent of missing data is considered sufficiently high, tipping point analysis may be repeated, imputing all missing microbiological responses at TOC, irrespective of the reason for missingness, using random draws from a binomial distribution as described above.

- 5) Primary analysis is based on Micro-ITT population using CLSI breakpoints. The ceftriaxone MIC breakpoints for *N. gonorrhoeae* currently differ between CLSI and EUCAST, if isolates are identified with different interpretations applying the EUCAST breakpoints as compared to CLSI, a sensitivity analysis of primary endpoint will be produced on a population defined based on EUCAST breakpoints (Micro-ITT EU). Ceftriaxone susceptibility will be evaluated by applying EUCAST MIC breakpoints to results from ceftriaxone agar dilution testing. If an agar dilution value is not available for ceftriaxone, CLSI disk diffusion breakpoints will be applied to results from ceftriaxone disk diffusion testing. The number and percentage of participants with culture-confirmed bacterial eradication of NG from the body site will be summarized at the TOC visit by treatment group along with the 95% Exact (Clopper-Pearson) CIs. The adjusted estimates of the difference in microbiological success rate for the two treatment groups (gepotidacin – ceftriaxone plus azithromycin) will be calculated and summarized with 2-sided 95% CI based on a stratified analysis (pooled strata) using Miettinen and Nurminen (MN) method. Non-inferiority and superiority will be tested as stated in Section 2.4.

Note that if data warrant, this analysis may be repeated on the Micro-ITT and Micro-ITT EU populations, but excluding participants whose ceftriaxone susceptibility is determined by disk diffusion.

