2.110.	ME	EFF_T1	Summary of Microbiological Outcome and Response of Urogenital Gonorrhoea at the TOC Visit by Other Subgroups (Phenotypic Subgroups -CLSI)	For urogenital site and NG in the other strata specified in RAP, including Sex and Sexual Orientation. Include phenotypic and genotypic subcategory analysis for subgroups including age, sex and sexual orientation, region, country and FDA region	DS, SAC

Efficacy: Tables					
No.	Population	IDSL / Example Shell	Title	Programming Notes	Deliverable
2.111	Micro-ITT	EFF_T1	Summary of Microbiological Outcome and Response of Urogenital Gonorrhea at the TOC Visit by Other Subgroups (Phenotypic Subgroups – EUCAST)	For urogenital site and NG in the other strata specified in RAP, including Sex and Sexual Orientation. Include phenotypic and genotypic subcategory analysis for subgroups including age, sex and sexual orientation, region, country	DS, SAC
2.112	ME	EFF_T1	Summary of Microbiological Outcome and Response of Urogenital Gonorrhea at the TOC Visit by Other Subgroups (Phenotypic Subgroups - EUCAST)	For urogenital site and NG in the other strata specified in RAP, including Sex and Sexual Orientation. Include phenotypic and genotypic subcategory analysis for subgroups including age, sex and sexual orientation, region, country and FDA region	DS, SAC
2.113	Micro-ITT EU	EFF_T1	Sensitivity Analysis of Microbiological Outcome and Response Rate of Urogenital Gonorrhea at the TOC Visit Using EUCAST Breakpoints	Only for urogenital site and NG. Conditional output: if the Micro-ITT EUCAST population is the same as the Micro-ITT population then this output does not need to be produced.	DS, SAC
2.201.	Micro-ITT Rectal, Micro-ITT Pharyngeal	EFF_T1	Summary of Microbiological Outcome and Response of Pharyngeal and Rectal Gonorrhea at the TOC Visit	Only for pharyngeal and rectal body site and NG	DS, SAC

CONFIDENTIAL

BTZ116577

Efficacy: Tables					
No.	Population	IDSL / Example Shell	Title	Programming Notes	Deliverable
2.202.	ME Rectal, ME Pharyngeal	EFF_T1	Summary of Microbiological Outcome and Response of Pharyngeal and Rectal Gonorrhoea at the TOC Visit	Only for pharyngeal and rectal body site and NG	DS, SAC
2.203.	Micro-ITT Rectal	EFF_T1	Summary of Microbiological Outcome and Response of Rectal Gonorrhoea at the TOC Visit by Actual Strata	Only for rectal body site and NG for Actual strata (sex and sexual orientation, age)	DS, SAC

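### SAP Section 4 defines the Micro-ITT EU population as a union with the primary population, so the EUCAST sensitivity analysis cannot exclude a primary-analysis participant whose isolate is EUCAST-resistant

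*SAP*

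**What the plan says.** Four parts of the current SAP bear on this.

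- **Section 4, Micro-ITT (primary).** Randomised and treated participants who "have confirmed NG isolated that is ceftriaxone-susceptible (based on CLSI breakpoints) from baseline culture of their urogenital specimen".
- **Section 4, Micro-ITT EU.** "All participants who meet the definition of the Micro-ITT population and any participants randomly assigned to study treatment who receive at least 1 dose" and have a baseline urogenital isolate that is ceftriaxone-susceptible by EUCAST. The notes under the population table say that susceptibility is judged by CLSI MIC breakpoints on agar dilution, with EUCAST MIC breakpoints used instead for Micro-ITT EU. CLSI disk diffusion is the fallback for both when there is no agar dilution value. If a participant has several isolates from one body site, all must be susceptible.
- **Section 7.1.6.2, item 5.** If isolates are classified differently under the two systems, "a sensitivity analysis of primary endpoint will be produced on a population defined based on EUCAST breakpoints (Micro-ITT EU"). This analysis has a stratified Miettinen-Nurminen difference, a 95% CI, and noninferiority and superiority testing.
- **Section 12.9.6, Table 2.113.** The output is conditional: "if the Micro-ITT EUCAST population is the same as the Micro-ITT population then this output does not need to be produced".

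The revision history in SAP Section 1 is used here only for background and for the direction in which the breakpoints differ. Under Amendment 1 an added CLSI population served a "sensitivity analysis for the primary analysis including isolates identified as resistant by EUCAST but susceptible by CLSI". Amendment 2 records that "ceftriaxone susceptibility determination has been changed to CLSI from EUCAST guidelines" for the primary population, and "Micro-ITT CLSI population amended to Micro-ITT EU population".

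**The concern.** A EUCAST sensitivity analysis should show whether the noninferiority conclusion holds when participants with EUCAST-resistant isolates are left out. Those are the participants in whom the comparator might be expected to do less well. Any comparator failures among them lower the comparator rate and so favour noninferiority. The Section 4 definition keeps all of them in, whatever the data show.

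Section 7.1.6.2 item 5 and the Section 4 notes describe a different set, one based on EUCAST breakpoints. Two programmers working from the same SAP could therefore build two different populations. If the literal definition is used, the check may return the primary analysis again and then drop out under the Table 2.113 note.

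**Working it through.** **Inputs.** Population definitions, notes and the all-isolates rule: SAP Section 4. Purpose and method of the sensitivity analysis: SAP Section 7.1.6.2 item 5. Output condition: SAP Section 12.9.6. Sample size, success rates and margin (200 per arm, 90% in both arms, -10%, one-sided 0.025): protocol Section 10.2.1. Ceftriaxone MIC reporting scale: SAP Section 12.4.2.

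**The plan's own figure.** Unpooled normal approximation: Φ(0.10/√(2 × 0.9 × 0.1/200) − 1.96) = Φ(3.333 − 1.960) = 0.915. This agrees with the stated power of about 91%. It is background only; the point below concerns who is in the set.

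**Step 1: can anyone leave?** Let C be the treated participants with CLSI-susceptible isolates (Micro-ITT) and E those with EUCAST-susceptible isolates. As written, Micro-ITT EU = C ∪ E, which contains C whatever the breakpoints are. A participant in C but not in E stays in. This follows from Section 4 alone.

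**Step 2: can anyone join?** Only participants in E but not in C. The documents give no numeric breakpoints. The revision history describes the discordant isolates as "including isolates identified as resistant by EUCAST but susceptible by CLSI". On one ordered MIC scale this puts the EUCAST susceptible cut-off below the CLSI one, so E lies within C and C ∪ E = C. The all-isolates rule preserves this at participant level. The disk-diffusion fallback uses CLSI criteria for both sets and cannot separate them.

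As a check, every pair of different cut-offs on the 14-value scale from 0.002 to 16 µg/mL was tried (14 × 13/2 = 91 pairs in each direction). With EUCAST below CLSI, the union differs from Micro-ITT in 0 of 91 pairs. With EUCAST above CLSI, it differs in 91 of 91.

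**Step 3: what happens to the output?** In the stricter-EUCAST case, discordant isolates trigger item 5, but the two populations are still identical, so the Table 2.113 note allows the table to be omitted.

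**Step 4: size of what could be missed.** Start from 180/200 in each arm, and take gepotidacin minus comparator.

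- Remove one comparator failure: 180/199 = 90.45%, so the difference moves by −0.45 percentage points.
- Remove one comparator success: 179/199 = 89.95%, so the difference moves by +0.05 percentage points.

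For an extreme illustration, assume k discordant participants per arm, all successes on gepotidacin and all failures on the comparator. The EUCAST-susceptible difference is then (180 − k)/(200 − k) − 180/(200 − k) = −k/(200 − k). Confidence intervals are unstratified Miettinen-Nurminen.

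| k per arm | Union as written: difference (95% CI) | EUCAST-susceptible only: difference, lower 95% limit |
|---|---|---|
| 1 | 0.0% (−6.05 to 6.05) | −0.5%, −6.53 |
| 2 | same | −1.0%, −7.02 |
| 5 | same | −2.6%, −8.49 |
| 8 | same | −4.2%, −10.01 |
| 10 | same | −5.3%, −11.05 |

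Under this extreme pattern the −10% margin is crossed at k = 8 but not at k = 5. The documents do not give k or the outcomes.

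**The case against.** **The information is not lost.** The Section 4 notes require narratives on populations, participants and isolates affected by the breakpoint difference. Table 2.320 gives success by baseline MIC under EUCAST, ceftriaxone included. Table 2.326 gives success by EUCAST interpretation. Table 2.111 covers EUCAST phenotypic subgroups, Table 2.344 baseline EUCAST resistance, and Listings 608 and 614 the individual EUCAST results. Sections 4 and 7 also allow outputs to be repeated on EUCAST-based populations. This stands. A reader might infer that the plan would hide any breakpoint issue, or that this is its only look at EUCAST; neither is supported. What remains is narrower: these displays are descriptive, the repeats are optional, and none of them specifies a noninferiority result in EUCAST-susceptible participants.

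**The notes and item 5 can be read as EUCAST-only.** That is true, so the finding is an inconsistency between sections rather than a settled plan to run the wrong set. It still has to be resolved, because Section 4 is where the population is defined.

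**The direction of discordance rests on the revision history.** This also stands. The entry describes an earlier SAP version, and Section 12.4.2 says that breakpoints can change and that the final database uses the latest ones. A reader might infer that the analysis must duplicate the primary; that holds only if EUCAST is the stricter cut. That nobody can be removed does not depend on it. The earlier Micro-ITT CLSI definition is not in the documents, so the view that the union wording is left over from it is inference.

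**The effect may be trivial.** It may be. A reader might take 0.45 points as the shift per participant, but it applies only to a removed comparator failure. With 1:1 randomisation, removals are expected in both arms and may largely offset.

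**Conclusion.** The Section 4 definition of Micro-ITT EU contradicts Section 7.1.6.2 item 5 and Section 4's own notes. As written, it removes no primary-analysis participant under any breakpoints. If EUCAST is the stricter cut, it also adds none. The one EUCAST-population noninferiority analysis that the SAP specifies in full would then equal the primary or be omitted.

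The numerical consequence cannot be fixed from the documents. With few discordant participants it is small; only the extreme pattern above, at about 8 per arm, would cross the margin. A reader might infer that the primary conclusion itself is at risk. It is not: the primary population, estimator, alpha, power and decision rule are unaffected. What is affected is whether a stated sensitivity analysis tests what it says it tests.

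**What to change.** Before unblinding, replace the Micro-ITT EU definition in SAP Section 4. It should cover participants who were randomised, received at least one dose, and have central-laboratory-confirmed NG from the baseline urogenital culture. Every baseline urogenital isolate should be ceftriaxone-susceptible by EUCAST MIC breakpoints on agar dilution or, where no agar dilution value exists, by CLSI disk-diffusion breakpoints. Delete the clause that brings in all Micro-ITT participants.

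The disk-diffusion fallback must stay. Section 12.4.2 states that there are no EUCAST disk criteria for this organism, so dropping it would exclude participants without an agar dilution value and conflict with item 5.

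The Table 2.113 condition can then stand, because the two populations would coincide only when no participant is classified differently. If rectal, pharyngeal or microbiologically evaluable outputs are repeated on EUCAST-based populations, build those sets from the same EUCAST-susceptible definition.

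The cost is one sentence and one population flag, with no change to the protocol, data collection or primary analysis. Made after unblinding, the same change could look data-driven.
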